### 7.2 Adverse Event Reporting

For this study, only Adverse Events (AEs) attributed to ultrasound use are reported.

During study procedures, the study coordinator reminds patient to contact the clinical care team, if they experience any symptoms during the exam or afterwards. If the participant expresses to the coordinator that they have experienced symptoms during or after the exam, the coordinator will alert the clinical care team on the same day to contact the patient for AE evaluation and management. During baseline through week 12, patient will continue with standard-of-care provider visits at or outside of Stanford (generally, every 2-6 weeks, at the discretion of the treating clinical care team) including adverse event management. At week 12, a retrospective chart review will document any undisclosed study-related late adverse events and assure there are no ongoing study-related adverse events. If there is no adequate information in the medical record at week 12, patient will be contacted if needed to complete this documentation. Therefore, at minimum, there is one documented AE evaluation at week 12.

AEs are graded according to CTCAE v5.0. Both Serious and Non-Serious study-related AEs are clearly noted in source documentation and listed on study specific Case Report Forms in RedCAP. The Protocol Director or designee assess each AE to determine whether it is unexpected according to the Informed Consent or Protocol Document and related to the investigation. All study-related Serious Adverse Events (SAEs) are tracked until resolution. AEs and SAEs related to standard-of-care procedures or medication, including the studied drug therapy for RCC, are not recorded or reported.

## 8. REGULATORY CONSIDERATIONS

### 8.1 Institutional Review of Protocol

The protocol, the proposed informed consent and all forms of participant information related to the study (e.g., advertisements used to recruit participants) must be reviewed and approved by the Stanford IRB and Scientific Review Committee (SRC). Any changes made to the protocol will be submitted as a modification to be approved by the IRB and SRC prior to implementation. The Protocol Director will disseminate the protocol amendment information to all participating investigators.

### 8.2 Data Management Plan

An alphanumeric study code is selected by the study coordinator for each participant. Source documents and analytic data are used to complete the electronic Case Report Forms (eCRFs) in the Stanford RedCAP database. An eCRFs needs to be completed for each enrolled patient and, at minimum, needs to contain the following data:

- study code
- age, race, ethnicity, sex, diagnosis, cancer stage, tumor histology, and drug treatment
- identification of lesions selected for ultrasound exams and for response evaluation
- identification of time points and modality of ultrasound exams and standard-of-care radiographic imaging
- tumor perfusion parameters quantified from ultrasound studies
- tumor diameter measurements quantified from standard-of-care radiographic imaging studies
- primary and secondary outcomes measures.

The digital ultrasound images including PHI may be stored on the ultrasound scanners for the duration for the study. Ultrasound image files that are transferred off the scanners have coded file names and the files are stored on [name] lab servers or using cloud storage services that are certified for PHI (e.g., Stanford Medicine Box). Other source documents need to be included in the regulatory binder. The Stanford's Data & Safety Monitoring Committee (DSMC) will routinely review the source documentation (incl. the raw imaging files on [name] lab servers) and verify the corresponding data entered in the eCRFs. All entered, changed, and final data shall be available with a validated audit trail or data extract report. The eCRFs shall be considered complete when all expected data has been entered and all discrepancies have been resolved or documented.

Source documents, other documents containing HIPAA identifiers, clinico-demographic or analytic data linked to the participants' identity (i.e., Protected Health Information, PHI), and information linking study codes to participant identities may be additionally maintained in paper form or electronically on co-investigators' computers or using cloud storage services that are certified for PHI

(e.g., OnCore, Stanford Medicine Box) until study completion. All computers need to comply with Stanford University IT security standards. Access to files and folders with PHI (paper or electronic) must be restricted to the study personnel.

Upon study closure, all PHI not stored in the regulatory binder (physical and electronic), regulatory database (i.e., OnCore), or eCRFs must be destroyed, for example by de-identifying the data and files in accordance with the HIPAA Privacy Rule. Ultrasound data must be removed from the ultrasound scanners upon study closure. However, ultrasound images with PHI may be retained in the electronic medical record at Stanford Healthcare at the discretion of the study radiologists as long as they are clearly designated as research data and not associated with a formal interpretation.

The Protocol Directors have ultimate responsibility for collection and reporting of all clinical safety and study data entered in the eCRFs and any other data collection forms (source documents) and ensuring that they are attributable, legible, contemporaneous (timely), original, and accurate as well as complete, consistent, and available when required.

### **8.3 Data and Safety Monitoring Plan**

During the clinical investigation, the Protocol Directors will evaluate the progress of the trial, including periodic assessments of data quality and timeliness, adherence to the data management plan, participant recruitment, accrual and retention, participant risk versus benefit, performance of trial sites, and other factors that can affect study outcome.

The Stanford Cancer Institute Data and Safety Monitoring Committee (DSMC) will audit study-related activities at least annually in accordance with the DSMC SOP to determine whether the study has been conducted in accordance with the protocol, local standard operating procedures, FDA regulations, and Good Clinical Practice (GCP). This may include review of regulatory binders, case report forms, eligibility checklists, and source documents. In addition, the DSMC will regularly review serious adverse events and protocol deviations associated with the research to ensure the protection of human subjects. Results of DSMC audits will be communicated to the IRB and the appropriate regulatory authorities at the time of continuing review, or in an expedited fashion, as needed.

## **9. MEASUREMENTS**

### **9.1 Primary Outcome Measures**

The primary endpoint is initial objective response per RECIST v1.1 assessed 8-16 weeks after start of treatment, using standard-of-care imaging. expressed as a number and proportion without dispersion.

Initial objective response (yes/no): defined as having either Complete Response (CR) or Partial Response (PR) per RECIST v1.1 at first on-treatment response evaluation 8-16 weeks after initiating treatment.

### 9.1.1 Measurement Methods

Tumor diameter measurements: Where possible, the same lesions that were selected for repeat LEAD ultrasound exams are used as target lesions for response evaluation per RECIST. Different lesions may be selected at the discretion of the radiologist designated to review response evaluation.

### 9.1.2 Measurement Time Points

At treatment 'baseline' (prior to starting treatment) and 12 weeks after start of treatment (+/- 4 weeks) standard-of-care radiographic imaging is performed for initial response evaluation.

No further follow-up is required for the primary endpoint.

### 9.1.3 Response Review

Response evaluation per RECIST v1.1 is reviewed by a designated radiologist, who may be the same person that performs the tumor diameter measurements.

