## 6. STUDY CALENDAR

	Pre-Study	Baseline (up to 28 days prior to initiating therapy) h	Standard-Of-Care Therapy			
			Week 3 (+/- 8 days) i	Week 6 (+/- 15 days) i	Week 12 (+/- 4 weeks) h	Before Study Completion j
Informed consent	X					
Doppler ultrasound exams a		X	X	X		
Standard-of-care imaging b	X				X	
Adverse event evaluation c				X		
Recording of age, race, ethnicity, sex, diagnosis, cancer stage, tumor histology, and drug treatment d,e				X (just once during any study timepoint)		
Documentation of lesions selected for ultrasound exam, scanners and modalities used, and imaged axis planes		X	X	X		
Quantification of tumor perfusion parameters f						X
Tumor diameter measurements g						X
Optional recording of medical history and other diagnoses, concurrent treatment and medication, additional treatment, follow-up, and survival data for future correlation studies e		X				X

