
a) Doppler ultrasound exams: power Doppler and LEAD ultrasound exams, performed during standard-of-care clinic visit or at research-only visit; if exam can be performed only with one of the two ultrasound scanners, only in one axis, or if one time point is missed entirely, subsequent exams may still be performed in full within their allowed time window.
 
b) Standard-of-care imaging: The baseline standard-of-care scan is generally within 6 weeks prior to initiating therapy, but may be greater than 6 weeks prior to therapy, if this is the scan that the treating physician chooses to use as reference for response evaluation. Preferably, this is a CT Chest-Abdomen-Pelvis (CAP) scan (with or without contrast), but it may also be an MRI or PET/CT or a combination of MRI and CT. At the discretion of the treating oncologist, the standard-of-care scan at week 12 may be performed outside of the +/- 4-week window.
 
c) Adverse event (AE) evaluation: Only AEs that are attributed to the study procedures are recorded and reported. During study procedures, study coordinator reminds patient to contact the clinical care team, if they experience any symptoms during the exam or afterwards. If the participant expresses to the coordinator that they have experienced symptoms during or after the exam, the coordinator will alert the clinical care team on the same day to contact the patient for AE evaluation and management. During baseline through week 12, patient will continue with standard-of-care provider visits at or outside of Stanford (generally, every 2-6 weeks, at the discretion of the treating clinical care team) including adverse event management. At week 12, a retrospective chart review will document any undisclosed study-related late adverse events and assure there are no ongoing study-related adverse events. If there is no adequate information in the medical record at week 12, patient will be contacted if needed to complete this documentation. Therefore, at minimum, there is one documented AE evaluation at week 12.
 
d) to be recorded once between baseline and study completion
 
e) may be obtained until study completion, even after a participant's death; patients or their outside medical providers may be contacted as needed to obtain the clinico-demographic data, if not available in the Stanford medical record.
 
f) to be quantified and recorded for all ultrasound exams from this study
 
g) RECIST measurements to be recorded for all imaging studies used for response evaluation (CT, MRI or PET/CT as described in footnote (b)). Performed at minimum at baseline and 12 weeks. RECIST measurements will also be recorded for other subsequent standard-of-care studies that the treating MD obtains at any interval to evaluate treatment response (until 12 months after initiating treatment or until end of the treatment that is being studied, whichever occurs first)
 
h) For combination treatments, initiation of therapy is typically defined by the day of starting treatment with the second drug, however another day (such as the start of treatment with the first drug) may be defined as start of treatment at the discretion of the Protocol Director; date considered start of treatment will be documented in the research procedure note in the electronic medical record.
 
i) 10 days is the minimum time period between week-3 and week-6 power Doppler ultrasound exams; similarly, 10 days is the minimum time period between week-3 and week-6 LEAD ultrasound exams; it is not required that power Doppler and LEAD ultrasound exams are performed on the same date.
 
j) Before end of study (3 years from date of study opening)
						

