#### Selection of lesions for LEAD ultrasound exams:

Before the first ultrasound exam, the treating medical oncologist, a Protocol Director, or a designated radiologist selects up to 5 lesions per patient (target lesions per RECIST v1.1). At the treatment 'baseline' LEAD ultrasound exam (up to 28 days prior to start of treatment), perfusion of these 5 lesions is measured. Additional lesions may be assessed at the discretion of the investigators, so that in the end up to 5 lesions are selected for repeat ultrasound exams that in the opinion of the investigators lend themselves to reproducible tumor perfusion measurements. LEAD ultrasound tumor perfusion measurements of the up to 5 lesions that were selected for ultrasound studies at the treatment 'baseline' exam are performed again 3 weeks (+/- 8 days) after start of treatment.

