#### Quantification of tumor perfusion parameters:

The following parameters are computed from the LEAD ultrasound measurements for each lesion:

- overall tumor perfusion: the integrated power within the tumor
- average red cell flux: the integrated power within the tumor normalized by tumor size
- tumor-to-background perfusion ratio: the ratio of the integrated power within the tumor to the integrated power in a same sized region in nearby healthy tissue.

Changes in tumor perfusion parameters after 3 weeks of treatment:

Defined as relative change in these parameters, i.e., difference between time points divided by value at time point 1, expressed as percentage. For determining the relative change in several lesions of the same patient, the average of the relative changes in the up to 5 individual lesions is calculated.

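### Perfusion may be quantified at any time before study completion, and neither the ultrasound nor the RECIST reading is masked to the other

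*Protocol*

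**What the plan says.** **Timing.** In the Section 6 calendar, the rows "Quantification of tumor perfusion parameters" and "Tumor diameter measurements" each carry a single mark, both in the last column (Before Study Completion). Footnote j defines that column as "Before end of study (3 years from date of study opening". Footnote f says perfusion is "to be quantified and recorded for all ultrasound exams from this study" and sets no deadline relative to the week-12 scan. Footnote g says of the RECIST measurements "Performed at minimum at baseline and 12 weeks".

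**Predictor.** Section 10.3.2 defines three parameters per lesion. All three use integrated power within the tumor. The tumor-to-background ratio also uses "the integrated power in a same sized region in nearby healthy tissue". The section does not say how these regions are delineated or by whom. Lesions are chosen before the first ultrasound exam: "the treating medical oncologist, a Protocol Director, or a designated radiologist selects up to 5 lesions per patient".

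**Outcome.** Section 9.1.1 makes the ultrasound lesions the RECIST targets where possible, but leaves the response radiologist free to choose others and does not say by when. Section 9.1.3 (repeated in 9.2.3) has response reviewed by a radiologist "who may be the same person that performs the tumor diameter measurements".

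**Masking.** None is stated. Section 2.6 describes the cohort as open-label. Section 8.2 gives coded file names to images moved off the scanners.

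**The concern.** The primary analysis relates week-3 change in LEAD perfusion to a response that each patient's care team learns around week 12. As the calendar stands, the perfusion values can be derived from stored images months or years after that response is known. Any judgement in outlining the tumor or placing the reference region can then lean, without intent, toward the known answer. The reverse path is also open: the response radiologist can settle target lesions and read the week-12 scan with the ultrasound results in view.

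Either path would make predictor and outcome agree better than they should. Section 10.7 takes an AUC of at least 0.7, in any predictive model, as the trigger for a follow-up study. The cross-validation in Section 10.3.2 gives no protection, because values read with knowledge of the outcome sit in every fold, held-out ones included.

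**Working it through.** The point rests mainly on the text. The arithmetic only shows what a given amount of reader bias would do.

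**1. Can quantification follow the response?** Yes. The only limit is the end of the study, 3 years from opening. Footnote g can be read as naming the scans to be measured or as the time of measuring them. On either reading, the limit for perfusion falls after week 12.

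**2. What is already fixed before response?**
- Ultrasound lesions are settled at the baseline exam, up to 28 days before treatment.
- The week-3 images are due by day 3 × 7 + 8 = 29.
- The response window opens at day 12 × 7 − 28 = 56.

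The images behind the primary predictor are therefore normally acquired before response is assessed. What stays open is the derivation of numbers from those images, the choice of RECIST targets, and the week-12 reading.

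**3. Does anything else close the gap?** Coded file names are a privacy measure. Section 8.2 lets study personnel hold the link between codes and identities, and images with identifiers may remain on the scanners. No section requires different people for the two readings.

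**4. The plan's own figures.** The protocol gives no figure for reader bias. Its one design figure, a margin of error of 0.14 for the AUC (Section 10.5), concerns precision. The Hanley-McNeil standard error at AUC 0.7 with 0.59 × 20 = 11.8 responders and 8.2 non-responders is 0.118, so the 95% half-width is 1.96 × 0.118 ≈ 0.23 and 0.14 is not reproduced. That is a separate matter, and this point does not depend on it.

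**5. Illustration at a true AUC of 0.70.** The model is binormal with one marker, and the shift sizes are assumptions.
- AUC = Φ(d/√2), so d = √2 × Φ⁻¹(0.70) = 0.742.
- Shift of 0.2 SD: Φ((0.742 + 0.2)/√2) = 0.747.
- Shift of 0.3 SD: Φ((0.742 + 0.3)/√2) = 0.769.
- The gains of 0.047 and 0.069 are 0.40 and 0.58 of the 0.118 standard error.

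**6. Illustration when perfusion carries no information.** Simulation of 40,000 studies, 12 responders against 8 non-responders, one marker, same kind of assumed shift:

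| Assumed shift (SD) | Apparent AUC | Studies with empirical AUC ≥ 0.7 |
|---|---|---|
| 0 | 0.50 | 6.7% |
| 0.25 | 0.57 | 16% |
| 0.50 | 0.64 | 32% |
| 0.74 | 0.70 | 51% |

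The planned model is a cross-validated Lasso on three parameters, averaged over up to five lesions, plus covariates. These figures show direction and rough scale only and do not predict the planned analysis.

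**The case against.** The strongest reply is that the protocol is silent rather than wrong. The last calendar column is an outer limit. It does not place quantification after response, and Section 2.4 even speaks of assessing perfusion in real time. Nothing says that the readers are unmasked or are one person. The lesions are settled at baseline and are the default RECIST targets, so the worst form of selection is already limited. A model that passes leads only to validation in an independent cohort.

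Much of this stands, and it limits the point. Four stronger readings that a reader might infer are not supported:
- **That one person reads both ultrasound and response.** The sentence in Section 9.1.3 covers measuring diameters and classifying response, both on the CT or MRI side.
- **That regions are placed by hand.** The protocol does not say whether delineation is manual, semi-automatic or automatic. The less judgement it involves, the smaller the risk.
- **That the AUC is biased.** The schedule permits late, unmasked quantification but does not require it. Nor can it be said that bias would carry a borderline model clear of 0.7: the shifts are assumed, and the gains in step 5 are about half a standard error.
- **That the AUC is the study's sole product.** Sections 9.2 and 10.4.2 also plan tumor-burden and per-lesion correlations and 12-month PFS.

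The reply does not remove the core. The calendar is a positive statement of when the predictor may be derived. Reader masking is a matter of study conduct that belongs in the protocol, not only in an analysis plan.

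**Conclusion.** The concern holds as a risk that the schedule permits, not as a bias shown to exist. Following the protocol as written, the primary predictor can be derived with the outcome known, and the outcome can be read with the predictor known. Either can bias the AUC upward against the 0.7 criterion. The size cannot be taken from the protocol. It depends on how much judgement enters the region delineation and the target-lesion choice, and the first of these is not described. The illustrations rest on an assumed shift and a single binormal marker. Baseline selection of ultrasound lesions, and their default use as RECIST targets, narrow the exposure but do not close it. This is a cheap improvement and no ground for faulting the design as a whole.

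**What to change.** - **Section 6 (calendar and footnote f) and Section 10.3.2:** state that perfusion is quantified from coded images by someone masked to response and clinical course. Lock the values before they are linked to response, or before the week-12 scan is read. State how the tumor and reference regions are delineated.
- **Sections 9.1.1 and 9.1.3:** state that RECIST target lesions are fixed from the baseline scan, including any that differ from the ultrasound lesions, and that the week-12 scan is read without the ultrasound values.
- **Values already derived without masking:** re-quantify them from the stored images under the same rule.

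The cost is a set order of work, a locked file, and giving quantification to a team member without access to response data. Coded file names help but do not mask by themselves. The protocol does not describe reader staffing, so whether such a person is already on the team has to be confirmed. No extra scan or visit is needed.

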## 9.2 Secondary Outcome Measures

Secondary endpoints are:

- 1) **initial relative change in tumor burden** (continuous): defined as relative change (i.e., difference between time points divided by value at time point 1, expressed as percentage) in the sum of all tumor diameters between treatment 'baseline' and first on-treatment response evaluation 8-16 weeks after start of treatment, using RECIST v1.1 for tumor diameter measurements, expressed as mean +/- standard deviation and median with interquartile range
- 2) **initial lesion response** (continuous): defined as the relative change in tumor diameter of a single lesion between treatment 'baseline' and first on-treatment response evaluation 8-16 weeks after start of treatment, using RECIST v1.1 for tumor diameter measurements, expressed as mean +/- standard deviation and median with interquartile range.
- 3) **12-month progression-free survival (PFS)** (yes/no): defined as not having experienced any PD per RECIST v1.1 within the first 12 months after initiating treatment (day 1 will be treatment start date), as a number and proportion without dispersion.

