## 2. BACKGROUND

### 2.1 Study Disease

Renal cancer is the 8th most common cancer in the U.S. and patients with metastatic RCC (mRCC) have a 5-year overall survival (OS) rate of 12%. There are 17 FDA-approved drugs for mRCC, which include TKIs of vascular endothelial growth factor receptor 2 (VEGFR2, a key mediator of angiogenesis), and antibodies that target immune checkpoint proteins such as programmed cell death protein-1 (PD-1), programmed death ligand-1 (PD-L1), or cytotoxic T-lymphocyte-associated protein 4 (CTLA-4).

In April 2019, the FDA approved the combinations of a TKI (axitinib) with an ICI (pembrolizumab or avelumab) for first-line treatment of mRCC and additional TKI plus ICI combination therapies (cabozantinib plus nivolumab, lenvatinib plus pembrolizumab) have been approved more recently. TKI plus ICI has become the new standard-of-care first-line treatment that improves OS for patients with mRCC.

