### **9.2.1 Measurement Methods**

Tumor diameter measurements: same as for primary endpoint

Progression-free survival: determined by medical record review and contacting participants or their outside medical providers as needed.

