### **9.2.2 Measurement Time Points**

Initial response evaluation is performed by radiographic imaging at the same timepoints as for the primary endpoint. For repeat response evaluations on treatment, standard-of-care restaging imaging studies will be used. These, as well as determination of 12-month PFS, require follow-up at 12 months after initiation of treatment.

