## 10.4 Secondary Analysis

### 10.4.1 Analysis Population

All patients who have completed at least one LEAD and Doppler ultrasound exam at any time point. For correlation analyses, patients are included for each analysis based on availability of data points for specific analyses. If fewer than 20 patients in arm 1 and 10 patients in arm 2 fulfill these criteria for any secondary analysis, additional patient may be enrolled at the discretion of the Protocol Directors to have a complete dataset from 20 and 10 patients for this analysis, respectively.

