### 10.4.2 Analysis Plan

To address our secondary objective, i.e., evaluating if there is an optimal ultrasound modality to predict initial objective response in arm 1, we will utilize the same analysis approach as outlined above for the primary analysis. Here, we will use change in tumor perfusion parameters at **6 weeks** as our independent variables and conduct two regression analyses: (1) using power Doppler measurements and (2) using LEAD ultrasound measurements. AUCs between the two models will be compared using the nonparametric approach of DeLong for correlated AUC curves. In addition, we will compare AUCs between these models to the predictive model for the primary analysis.

To assess if there is an optimal time point for predicting initial objective response in arm 1, we will conduct Lasso regression models using tumor perfusion parameters for each time point (treatment 'baseline', 3 weeks, 6 weeks) separately for each imaging modality using a similar approach as outlined above. Given the exploratory nature of these analyses, we will not adjust for multiple testing.

For each arm, we will conduct correlation analysis for change in perfusion parameters at 3 and 6 weeks and initial relative change in tumor burden (overall and per-lesion), initial overall response, best overall response, and PFS until 12 months after initiating treatment by calculating either the Pearson r or Spearman rank correlation, as appropriate. PFS is estimated using the Kaplan-Meier method and the Kaplan-Meier curves will be presented.

Selection of lesions for ultrasound exams:

The up to 5 lesions that were selected for ultrasound studies for the primary analysis are re-assessed 6 weeks (+/- 15 days) after start of treatment and each lesion is assessed with both LEAD and power Doppler ultrasound at all 3 time points (treatment 'baseline', 3 weeks, and 6 weeks after initiating treatment).

Quantification and change of tumor perfusion parameters: defined in the same way as for the primary analysis for both power Doppler and LEAD ultrasound.

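### The 12-month progression-free survival endpoint names only RECIST progression as failure, so a patient who dies within 12 months without documented progression can be scored progression-free

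*Protocol*

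**What the plan says.** The protocol lists 12-month progression-free survival (PFS) as its third secondary endpoint (section 9.2). It is a yes/no variable, "defined as not having experienced any PD per RECIST v1.1 within the first 12 months after initiating treatment", reported as a number and a proportion. Death does not appear in the definition.

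The other places that deal with PFS do not add it:

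- Section 1.2 names the endpoint and the list of abbreviations expands the term; neither defines an event.
- Section 9.2.1 gives the source of PFS status: "determined by medical record review and contacting participants or their outside medical providers as needed".
- Section 9.2.2 says that repeat response evaluations, "as well as determination of 12-month PFS, require follow-up at 12 months after initiation of treatment".
- Section 10.4.1 sets the population: "For correlation analyses, patients are included for each analysis based on availability of data points for specific analyses".
- Section 10.4.2 correlates perfusion change with "PFS until 12 months after initiating treatment by calculating either the Pearson r or Spearman rank correlation", and adds that "PFS is estimated using the Kaplan-Meier method and the Kaplan-Meier curves will be presented". It names neither the event nor a censoring rule.

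The study calendar (section 6) places survival data in an optional row intended for later correlation work. Its footnote e says that such data "may be obtained until study completion, even after a participant's death". Nothing links that row to the PFS endpoint.

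**The concern.** The name and the definition describe different quantities. The name promises that the patient is alive and without progression at 12 months. The definition asks only whether RECIST progression was recorded.

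The two part company for a patient who dies before a scan shows progression. Under section 9.2.2, progression after the first evaluation is picked up on standard-of-care restaging scans, so a patient who deteriorates and dies between scans may have no documented progression. That patient satisfies the definition as worded, although the outcome is the one that a PFS endpoint is meant to count as failure.

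Two results could be affected. One is the reported 12-month PFS proportion in each arm. The other is the exploratory correlation of perfusion change with PFS. If that correlation uses the yes/no variable, such a death would sit in the good-outcome group. Section 10.4.2 does not say which form of PFS is used, so this second effect is conditional.

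**Working it through.** The protocol states no PFS rate, event count or precision for this endpoint, so there is no figure to reproduce. The check has two parts: what the sections say together, and a count.

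**Does any section override the definition?**

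- 9.2.1 says where PFS status comes from, not what counts as an event.
- 9.2.2 requires follow-up at 12 months. A patient who died in month 5 cannot be seen at 12 months, so one reader could call that patient not evaluable. Another could say that the status is fully known from the record: no progression was ever documented. The text does not choose.
- 10.4.1 includes patients according to available data. Under the definition in 9.2, a patient who died without progression has an available value, which is yes. The rule therefore does not clearly remove the patient.
- 10.4.2 is silent on the event.

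No section makes death a failure.

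**Inputs for the count**

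- N = 20 in arm 1 and up to 10 in arm 2 (Protocol Synopsis). These are nominal: 10.4.1 allows further enrolment, and arm 2 may be smaller.
- P = patients with documented progression within 12 months. Not given.
- D = deaths within 12 months without documented progression. Not given.

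**Formulas**

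- As defined in 9.2: (N − P)/N
- With death as failure: (N − P − D)/N
- Overstatement: D/N, whatever the value of P

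**Results**

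| Arm | N | D = 0 | D = 1 | D = 2 |
|---|---|---|---|---|
| 1 | 20 | 0 points | 1/20 = 5 points | 2/20 = 10 points |
| 2 | 10 | 0 points | 1/10 = 10 points | 2/10 = 20 points |

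Illustration for arm 1, assuming P = 8 and D = 2:

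- as defined: (20 − 8)/20 = 60%
- with death as failure: (20 − 8 − 2)/20 = 50%
- with the two deaths set aside as not evaluable: (20 − 8 − 2)/(20 − 2) = 10/18 = 55.6%

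The not-evaluable reading is thus milder, but in this example it still lies 5.6 points above the figure that counts death as failure. P and D here are assumptions, chosen only to show the mechanism.

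**The case against.** The strongest reply has five parts.

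**The literal reading is not the only one.** The wording in 9.2.2 and 10.4.1 leaves room to treat a patient who died as not evaluable. This stands, and it is why the point says that the patient can be scored progression-free, not that the patient will be. It does not remove the problem: neither section states such a rule, and setting these patients aside would discard failures.

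**Event and censoring rules belong in the statistical analysis plan.** For the Kaplan-Meier estimate this is fair. A reader might infer from 9.2 that death is not a failure in the Kaplan-Meier curves either. Section 10.4.2 says nothing on the event, and silence does not establish that. The reply does not reach the yes/no endpoint, for which the protocol itself fixes the event.

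**The correlation may not be affected.** A reader might infer that every such death lands in the good-outcome group. Section 10.4.2 does not say that the yes/no variable is used. If a PFS time is used, an early death could enter as a short time.

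**The size is unknown.** A reader might turn the background statement in 2.1, that "patients with metastatic RCC (mRCC) have a 5-year overall survival (OS) rate of 12" per cent, into a bias estimate. A constant hazard gives 12-month mortality of 1 − 0.12^(1/5) = 34.6%. If 10% to 30% of those deaths lacked documented progression, the overstatement would be 3.5 to 10.4 points; at half that mortality, 1.7 to 5.2 points. Only the 12% comes from the protocol, and it describes metastatic disease in general. The constant hazard, the share without documented progression and the halving are all assumed. These ranges are therefore not offered as findings; only D/N is derivable.

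**The stakes are low.** Section 10.1 makes all secondary endpoints exploratory, and no PFS target or decision rule exists. This stands and limits the weight of the point.

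Calendar footnote g may also end RECIST recording when the studied treatment ends. That concerns how progression is ascertained; it is a separate matter and does not support this point.

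**Conclusion.** The point holds in a limited form. Section 9.2, item 3 states a rule that does not match the name of the endpoint: it omits death, and no other section supplies it. A patient who dies within 12 months without documented progression meets the definition as worded and can be counted as a success.

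The size is D/N: 5 points for each such death at N = 20 and 10 points at N = 10, if the patient stays in the denominator and is scored yes. D is not given and may be zero. An effect on the perfusion-PFS correlation follows only if the yes/no variable is the one used.

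The primary analysis (section 10.3.2) and the criterion of an AUC of at least 0.7 for a follow-up study (section 10.7) concern initial objective response and are untouched. The correction is worth making because the rule is explicit and cheap to repair, and because in arms of 20 and 10 a single misclassified patient visibly moves the proportion.

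**What to change.** 1. In section 9.2, item 3, define failure as progression per RECIST v1.1 or death from any cause within 12 months of treatment start.
2. In section 10.4.2, state that the Kaplan-Meier estimate and the correlation use this same event, and say whether the correlation uses the yes/no variable or the PFS time.
3. Make vital status at 12 months a required data item, obtained through the record review and contact already described in section 9.2.1.
4. Reconcile the study calendar row that treats survival data as optional and for later correlation work. Once death is an endpoint event, that row cannot remain the only place where it is recorded.

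Cost: a phrase in 9.2, a clarification in 10.4.2, one added data item and a calendar correction. Reported PFS may be slightly lower. No new study procedure is needed, and the primary analysis and sample size do not change.
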